PER ^b -3			4mg	4mg	4mg	4mg	4mg	4mg
Partial NP ^c			X	X		X	X	
Full NP ^d	X	X			X			X
TEAEs ^e	X	X	X	X	X	X	X	X

Testing is at the end of each week.

^aBL = baseline visit.

^bPER = perampanel.

^cPartial NP = partial neuropsychological battery on non-clinic visit weeks refers to online CNS-Vital Signs computerized cognitive tests and behavioral questionnaires (POMS-total, AEP, & QOLIE-89 cognitive scores, which will be mailed back).

^dFull NP = full neuropsychological battery includes Non-computerized cognitive tests and the Partial NP (questionnaires and online CNS-Vital Signs computer tests).

^eTEAEs = treatment emergent adverse events.

The investigative team will monitor each subject's progress and safety during ASM treatment periods. Subjects will remain in their treatment arm for a total of 6 weeks.

D. Enrollment Goals

Previous studies indicate that an enrollment of 103 subjects will be required to obtain 76 evaluable subjects. See Statistical Section for power analysis.

E. Visit-Specific Treatment and Evaluation Sequence

Subjects will be randomly assigned to one of four possible titration schedules. Each titration schedule lasts 6 weeks.

At all visits, subjects will be advised on drug compliance and avoidance of medications which may adversely effect the results of cognitive function testing. Adverse events will be documented on the appropriate case report form. Appointments will be made for follow up visits and care will be taken to schedule all cognitive and behavioral function testing for a given subject at the same time of the day. Dosing of the study medication should be at approximately the same time of day (e.g., before the participant goes to sleep). However, due to the long half-life of perampanel, this is not critical. The time of testing and time of last 2 doses will be recorded.

The timetable for the study is listed in Appendix A. This is a visit-by-visit description of the events scheduled for each visit.

Visit 1 Screening Visit (-1 weeks prior to randomization)

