Subjects will be screened to assure they meet all of the inclusion criteria and none of the exclusion criteria. All eligible subjects will be required to give informed consent. A complete history, full physical examination, full neurologic examination, vital signs, laboratory screening (including urine pregnancy test for women of childbearing potential), urine drug screen, IQ screen with Peabody Picture Vocabulary Test, full cognitive battery (see below), and lifetime assessment of suicidal ideation/behavior measured by the Columbia-Suicide Severity Rating Scale (C-SSRS) will be obtained.

Visit 2 Baseline/Randomization (Study week 0)

At this visit all subjects who had successfully completed all screening tests and had no significant abnormalities on baseline laboratory, physical exam, neurologic exam, or IQ testing will be randomized to study drug. At this visit, neuropsychological testing will be conducted before the first dose of study drug is administered. Subjects will be randomized and study drug will be dispensed.

Visit 3 Home testing (Study week 1)

At this visit, a partial neuropsychological assessment of cognitive function and behavioral testing will be performed. The assessments at this visit consist of online CNS-Vital Signs computerized cognitive tests and behavioral questionnaires (Profiles of Mood States

(POMS), Adverse Events Profile (AEP), & cognitive/behavioral subsets of QOLIE-89). Partial neuropsychological assessment will be conducted. Telephone contact will be made to check on adverse events and to encourage compliance.

Visit 4 Home testing (Study week 2)

At this visit, a partial neuropsychological assessment of cognitive function and behavioral testing will be performed. The assessments at this visit consist of online CNS-Vital Signs computerized cognitive tests and behavioral questionnaires (Profiles of Mood States (POMS), AEP, & cognitive/behavioral subsets of QOLIE-89). Partial neuropsychological assessment will be conducted. Telephone contact will be made to check on adverse events and to encourage compliance.

Visit 5 Clinic testing (Study week 3)

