Subjects will be instructed to limit alcohol consumption to no more than ½ ounce of absolute alcohol equivalents per day (approximately one 12 oz. beer, or 1 mixed drink) and no more than 3 ounces per week. Regular consumption of caffeine is allowed but will be limited to two cups on test days. Subjects will be instructed not to consume alcohol 12 hours prior to cognitive and behavioral testing, , or take any over-the-counter medications for at least 72 hours prior to cognitive and behavioral testing. All concomitant medications will be recorded on the case report forms. Any concomitant medications and other agents, which are known to affect perampanel or have significant effects on cognition may not be taken during this trial. A partial list of examples include: anticholinergics, anticoagulants, antidepressants, antiepileptics, antipsychotics, anxiolytics, central nervous system depressants, corticosteroids, doxycycline, erythromycin, H2 antagonists, lithium, methylphenidate, narcotics, quinidine, reserpine, theophylline, and centrally active antihistamines.

IX. CLINICAL AND LABORATORY MEASUREMENTS

A. Clinical Efficacy Measurements (Study weeks -1, 0, 1, 2, 3, 4, 5, & 6)

Neuropsychological testing will be completed at screening (visit 1; study week -1), baseline (visits 2; study week 0), and each week of the ASM treatment period (visits 3-8; study weeks 1-6). The neuropsychological test results from the first screening testing (i.e., visit 1 at -1 weeks) will not be included in the analyses. All subjects will have at least 7 hours of sleep on the evening before the day of cognitive testing. (Note. If the subject does not get the required hours of sleep or takes non-approved medication, caffeine, etc., cognitive and behavioral testing will be rescheduled).

For detailed information regarding all of the cognitive tests refer to Section VII.

B. Clinical Safety Measurements

1. Physical Examinations (Study weeks -1, 3, & 6)

A complete physical and neurological examination will be performed during pre-study screening (visit 1; study week -1) and at the completion of the study (visit 8; study week 6) or early study discontinuation. Brief physical and neurological examinations will be performed at visit 5 (study week 3).

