 - d. Consent is withdrawn. Subjects will be encouraged to complete the study, although they may withdraw at any time without prejudice.
4. Subject replacement.

Subjects who are dropped from the study prior to completion of all cognitive testing will not be replaced.

Subjects who are withdrawn prior to completion of at least one set of cognitive testing on treatment drug (i.e., prior to visit 5/study week 3) may be replaced.

5. Follow-up of discontinued patients

Subjects who receive study drug and are discontinued from the study will have all safety assessments completed, including a complete physical examination and laboratory evaluation including chemistry, hematology with differential, urinalysis and urine pregnancy test as required at study termination. This testing should be done as soon as possible. Medical follow-up of any severe adverse events or clinically significant abnormal laboratory values will continue until the abnormality resolves, and adequate medical explanation is apparent. Such data will be provided to Eisai.

X. STATISTICAL EVALUATION

A. Sample Size

We assume that the 4 groups (3 PER treatments and a placebo group) are equally spaced (in terms of z-score) at the time point of maximum drug effects (end week 1 for 4mg group and end week 3 for titration to 2mg x2wks then 4mg group), with a maximum difference of 0.24 (which is the difference between the placebo group and treatment at max effect). We then assume that over the 4 visits after max drug effect the z-scores get closer together until

they are equal at the treatment week 6th. The calculation indicates that at least 18 subjects are needed in each group to have 80% power. Since there are 4 groups, the total sample at least finishing assessment at end of week 6 (event 8) would be $19 \times 4 = 76$. Enrollment will include 20% (n=15) more to account for dropouts prior to assessment at end of visit 2 (baseline), and ~15% (n=12) more for dropouts before end of event 8 (treatment week 6). Thus, the total enrollment sample will be 103 subjects.

In summary, the 4 total groups (3 PER treatment, 1 placebo) would need at least 19 subjects per group (76 total), and total enrollment would be rounded to 105 to account for dropouts.

B. Methodology for statistical analysis

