The parameters of interest are listed in Section VII. Descriptive statistics will be used to provide an overview of the primary, secondary, and other variable results. For categorical parameters, the number and percentage of subjects in each category will be presented. The denominator for percentages will be based on the number of subjects appropriate for the purpose of analysis. For continuous parameters, descriptive statistics will include number of subjects, mean, standard deviation (SD), median, minimum, and maximum. Unless otherwise specified, baseline neuropsychological data will be based on the Visit 2 assessments.

Study question 1: What are the behavioral, cognitive or other side effects of perampanel at different titration rates in healthy volunteers?

The primary outcome variable will be the overall neuropsychological composite z-scores for the objective and subjective measures combined.

Study question 2: What is the time course of habituation to objective vs. subjective neuropsychological (e.g., cognitive and behavioral) side effects of perampanel?

The primary outcome variable will be the neuropsychological composite z-scores for the objective and subjective measures, which will be analyzed separately.

The objective measure z-score will be calculated by averaging overall computerized and noncomputerized cognitive z scores, which are calculated by averaging individual z-scores of selected performance measures from the computerized cognitive test battery (i.e., average of z-scores for the domain scores for executive function and for processing speed) and from the noncomputerized cognitive test battery (i.e., average of individual z-scores for MCG immediate, MCG delayed, SDMT, and Stroop-average score). The subjective measure z-score will be calculated by averaging the individual z-scores for AEP, POMS, and QOLIE-cognitive questions (average of 3 scores from QOLIE). These z-scores will be assessed by a 4 (titration rate) \times 6 (time: weeks 1-6) ANCOVA controlling for scores at Baseline (visit 2) using an intent-to-treat analysis for those receiving neuropsychological testing at least at the end of week one. Imputations will be employed for dropout after week one.

We will control for differences across groups in age, gender, and personal/family history of psychiatric disorders.

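### Section IX.E.4 dates the first on-drug test set at week 3, but testing starts at week 1; sections X.B and X.D then disagree on whether subjects who leave in between are analysed

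*Combined protocol and SAP*

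**What the plan says.** Section numbers are those in the body of the protocol, which differ from the table of contents.

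- **Replacement (IX.E.4).** The first sentence reads "Subjects who are dropped from the study prior to completion of all cognitive testing will not be replaced". The next says that those withdrawn before completing "at least one set of cognitive testing on treatment drug (i.e., prior to visit 5/study week 3) may be replaced".
- **Testing schedule (VI.E, IX.A).** The first on-drug assessment is listed as "Visit 3 Home testing (Study week 1"), where "a partial neuropsychological assessment of cognitive function and behavioral testing will be performed". Section IX.A places testing at "each week of the ASM treatment period (visits 3-8; study weeks 1-6"). Appendix A agrees.
- **Batteries (VI.C, footnotes).** Weeks 1 and 2 use the partial battery (computerized tests and questionnaires). The "full neuropsychological battery includes Non-computerized cognitive tests and the Partial NP"; its first on-drug use is visit 5.
- **Analysis set (X.B).** The primary analysis is intent-to-treat "for those receiving neuropsychological testing at least at the end of week one", with imputation for later dropout.
- **Analysis sets (X.D).** The primary analysis takes completers and those with one on-drug test set, in nearly the same phrase as IX.E.4. People who stop early contribute the visits they attended. Intent-to-treat, however, requires both baseline and end-of-drug-period scores, and imputation is ruled out.
- **Assumed peak (X.A).** Maximum effect is placed at "end week 1 for 4mg group and end week 3 for titration to 2mg x2wks then 4mg group". No peak is given for the arm that moves to 4 mg after one week.

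Nothing says whether a replaced subject's data are kept.

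**The concern.** The parenthesis in IX.E.4 treats visit 5 as the first on-drug test set, two visits after on-drug testing begins. A subject who completes week 1 or week 2 and then leaves is replaceable under that date, yet already belongs to the X.B analysis set.

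This matters because the replaceable window is not neutral between arms. On the plan's own assumption, the arm starting at 4 mg reaches its peak effect at week 1, inside the window; the two-week titration arm peaks at week 3, at its edge. Section IX.E lets the investigator discontinue a subject for clinically significant adverse experiences, so leaving can be related to outcome. If early leavers then fall out of the analysis through X.D, the scores lost from the 4 mg arm could include some of its worst at the time of greatest assumed effect. Titration rate is the question the trial asks.

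**Working it through.** **1. The plan's own enrolment figure.** From X.A: 4 × 19 = 76; 20% of 76 = 15.2, taken as 15; 15% of 76 = 11.4, taken as 12; 76 + 15 + 12 = 103. The stated 103 is reproduced. The 12 are meant to cover dropout before week 6. No arm-specific dropout rate and no SD are given, so the bias can only be shown as a range.

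**2. One subject under each rule.** Take a subject tested at weeks 1 and 2 who leaves before visit 5.

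| Rule | Outcome for this subject |
|---|---|
| IX.E.4, first sentence | Not replaced: testing incomplete |
| IX.E.4, second sentence, by test set | Not replaceable if a partial battery is a set |
| IX.E.4, second sentence, by date | May be replaced: left before visit 5 |
| X.B intent-to-treat | Included, later weeks imputed |
| X.D primary analysis | Included if a partial battery is a set, otherwise not |
| X.D early discontinuation | Attended visits used |
| X.D intent-to-treat | Excluded, if the end of the drug period means week 6 |
| X.D missing data | No imputation |
| X.D safety set | Included: took a dose and gave follow-up |

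The test-set and date conditions, which IX.E.4 presents as equivalent, disagree for this subject unless a set means the full battery. X.B and X.D also disagree.

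**3. Size if the data are removed.** Let p be the proportion of an arm that leaves between weeks 1 and 3, and d the amount by which their week-1 z-score is worse than that of those who stay (mean m). The mean of the whole arm is (1 − p)m + p(m − d) = m − pd. Without the leavers it is m, so the arm looks better by pd. Both inputs are assumptions:

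- p = 0.10, d = 0.5: 0.05 z; 0.05/0.24 = 21% of the planned maximum difference.
- p = 0.20, d = 0.5: 0.10 z; 0.10/0.24 = 42%.

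Over a wider range, with k leavers among 19 and shift = (k/19) × d:

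| k | d = 0.24 | d = 0.5 | d = 1.0 |
|---|---|---|---|
| 1 | 0.013 (5%) | 0.026 (11%) | 0.053 (22%) |
| 2 | 0.025 (11%) | 0.053 (22%) | 0.105 (44%) |
| 3 | 0.038 (16%) | 0.079 (33%) | 0.158 (66%) |

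Percentages are of 0.24. The contrast between arms A and B moves by p_A·d_A − p_B·d_B, which is zero if leaving is equally frequent and equally related to score in both. The figures above are therefore contrasts against an arm with no such loss.

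**4. Size if the data are kept.** An arm was simulated by recruiting until 19 subjects reach week 3, with week-1 scores of 0 for those who stay and −0.5 for leavers, and all scores retained.

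| Early dropout | True week-1 mean | Mean with replacement, data kept |
|---|---|---|
| 5% | −0.025 | −0.024 |
| 15% | −0.075 | −0.072 |
| 25% | −0.125 | −0.120 |

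The largest discrepancy is 0.005 z, about 2% of 0.24 (0.005/0.24). Replacement itself is nearly harmless; removal of data is what matters.

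**The case against.** The strongest reply is that replacement adds a subject and deletes none. X.B keeps anyone tested at week 1, and X.D uses the visits attended by those who stop early. On that reading step 4 applies and there is almost no bias. This stands, and it rules out the stronger inference that the replacement rule in itself favours fast titration. What it does not remove is the X.D intent-to-treat definition, which staff could follow faithfully and so exclude these subjects, replaced or not.

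A reader might also infer that the secondary comparison of dropouts due to TEAEs is biased. The documents do not support that: the X.D safety set holds anyone who took a dose and gave follow-up information, so a treated subject who left at week 2 would still be counted.

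Nor is the week-3 date necessarily a slip. Visit 5 is the first on-drug full battery, and week-1 scores lack the paragraph memory, SDMT and Stroop tests that the X.B objective composite averages in. The set may mean a full set. IX.E.4 does not say so, however, and carrying that meaning into the near-identical phrase in X.D would drop subjects whom X.B includes.

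The two replacement sentences can likewise be read as a rule and its exception, so they are poorly joined and not flatly contradictory.

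Finally, the illustrative inputs are generous. A gap of 0.5 z is about twice the planned maximum effect, 20% loss in two weeks exceeds the roughly 15% planned through week 6, and the shift concerns one week of a six-week ANCOVA. These criticisms of the size stand.

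**Conclusion.** The inconsistency is real and should be repaired: the IX.E.4 cutoff does not match the testing schedule or the week-1 rule in X.B, and X.D can exclude subjects whom X.B includes. The effect on the results is conditional. It requires that subjects leaving between weeks 1 and 3 be excluded from the analysis, and that they be more frequent or score worse in the arm starting at 4 mg. The documents establish neither. If both hold, that arm's effect could be understated, by 0.05–0.10 z at week 1 under the 10–20% and 0.5 z assumptions and by 0.013–0.158 z over the wider grid. If the data are kept, the bias is near zero. A reader should not conclude that the plan as written favours fast titration.

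**What to change.** 1. In IX.E.4, move the cutoff to visit 3/week 1 to match X.B. Alternatively keep visit 5, and state that the set meant there is the full battery and that this meaning applies to replacement only.
2. Join the two IX.E.4 sentences as a general rule of no replacement followed by its one exception.
3. Reconcile X.D with X.B, including a single missing-data rule. State that every randomized subject with any on-treatment test stays in the intent-to-treat primary analysis, and every treated subject stays in the TEAE and dropout analyses, whether or not replaced.

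The retention statement in item 3 removes the bias risk whichever meaning of the test set was intended. The cost is a few sentences in IX.E.4 and X.D. With the week-1 cutoff slightly fewer subjects qualify for replacement, and those losses fall on the 12 already allowed for dropout before week 6.

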Subjects who have active suicidal ideation (answering “Yes” to questions 4 and/or 5 on the C-SSRS) will be evaluated by the Investigator. If the Investigator determines that a subject is at risk of suicide or self-harm, appropriate measures to ensure the subject’s safety and obtain mental health evaluation must be implemented and the Investigator should evaluate if the patient should be discontinued from the study.

This is a safety measure and is not used in the primary analysis.

2g. Adverse Events Profile (AEP)

The AEP measures patients' perception of adverse effects of antiepileptic drugs (Baker et al, 1997; Perucca et al, 2012). It has 19 items assessing the frequency of the most common adverse effects of antiepileptic drugs during previous weeks, using a four-point Likert scale. Item ratings can be added to obtain a total score of 19–76, higher scores indicating a greater burden of adverse effects.

2h. QOLIE-89

The QOLIE-89 inventory was developed to assess perception of quality of life issues in patients with epilepsy (Devinsky et al., 1995). It has 89 questions covering 17 different scales: health perceptions, overall quality of life, physical function, role limitations-physical, role limitations-emotional, pain, work/driving/social function, energy/fatigue, emotional well-being, attention/concentration, health discouragement, seizure worry, memory, language, medication effects, social support, and social isolation. These scales also are aggregated into an overall score. In the present study, we will employ only questions related to the subject's perception of their attention/concentration, memory, and language (Perrine et al., 1995; Elixhauser et al., 1999). The purpose of these measures in the present study is to allow us to compare subjective perceptions of cognitive side effects to objective performances (Marino et al., 2009). Where appropriate, ratings will be made based on the previous week, rather than previous 4 weeks as originally written in the QOLIE-89.

VIII. STUDY MEDICATIONS

A. Description

PER 2mg, 4mg, and placebos will be provided by Eisai or their designee. All ASM doses and placebos will be overencapsulated in matched opaque capsules.

B. Packaging and Labeling

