APPENDIX A - STUDY TIMETABLE

Event	1	2	3	4	5	6	7	8
Week	Screen ^a -1	BL ^b 0	1	2	3	4	5	6
Day ^c	-7	0	7	14	21	28	35	42
Clinic Visit	X	X ^m			X			X
Home Testing			X	X		X	X	
Informed Consent	X							
PMHx & Fam Hx ^d	X							
Vital Signs	X				X			X
Full PE ^e	X							X
Neuro Exam ^f					X			
CBC & Chems ^g	X							X
PER Level ^h					X			X
Urine drug screen	X							X
Urine pregnancy test ⁱ	X							X
C-SSRS ^j	X				X			X
Partial NP ^k			X	X		X	X	
Full NP ^l	X	X			X			X
TEAEs	X	X	X	X	X	X	X	X
Dispense Drug		X						

^aScreening visit may occur 1-3 weeks prior to baseline visit.

^bBL = baseline visit.

^cVisits may occur +/- 3 days from target day.

^dPMHx & Fam Hx = psychiatric history for subject and their family

^ePE = complete physical exam including full neurologic exam

^fNeuro Exam = brief neurological exam including brief physical exam

^gCBC & Chems = CBC with differential and Chemistries (comprehensive metabolic panel)

^hPER Level = perampanel blood level

ⁱWomen of childbearing potential only

^jC-SSRS = Columbia-Suicide Severity Rating Scale

^kPartial NP = partial neuropsychological battery on non-clinic visit weeks refers to online CNS-Vital Signs computerized cognitive tests and behavioral questionnaires (POMS-total, AEP, & QOLIE-89 cognitive scores, which will be mailed back). Note phone calls will be made for each home testing visit to assure adherence to the protocol.

^lFull NP = full neuropsychological battery includes non-computerized cognitive tests and the items from the Partial NP (questionnaires and online CNS-Vital Signs computer tests). Peabody Picture Vocabulary Test (PPVT) given only at screening visit.

^mThis week does not require clinic room or to see physician unless necessary.

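### X.B has no test of the objective-versus-subjective difference that study question 2 asks about, and its weekly objective score includes tests given on treatment only at weeks 3 and 6

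*Combined protocol and SAP*

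**What the plan says.** Study question 2, restated in Section X.B, begins "What is the time course of habituation to objective vs. subjective neuropsychological". Section VII.B 2h says the QOLIE-89 items are included to "allow us to compare subjective perceptions of cognitive side effects to objective performances". For this question X.B names as primary outcome the "composite z-scores for the objective and subjective measures, which will be analyzed separately".

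X.B then defines the score: "The objective measure z-score will be calculated by averaging overall computerized and noncomputerized cognitive z scores". The computerized half is the mean of the executive-function and processing-speed domain scores. The non-computerized half is the mean of MCG immediate recall, MCG delayed recall, SDMT and Stroop. The subjective score averages AEP, POMS and the QOLIE cognitive items. The model crosses four titration groups with six weeks: "time: weeks 1-6) ANCOVA controlling for scores at Baseline (visit 2".

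The schedule differs by week. In Section VI.C, footnote c, the "partial neuropsychological battery on non-clinic visit weeks refers to online CNS-Vital Signs computerized cognitive tests and behavioral questionnaires". In Appendix A, footnote l, the "full neuropsychological battery includes non-computerized cognitive tests and the items from the Partial NP". The full battery is given at screening, visit 2, week 3 and week 6. Weeks 1, 2, 4 and 5 have the partial battery.

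Section X.A places the maximum drug effect at "end week 1 for 4mg group and end week 3 for titration to 2mg x2wks then 4mg group".

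**The concern.** There are two gaps, and both affect the habituation result.

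**No direct comparison.** The question sets objective against subjective, yet no joint model, contrast or domain interaction appears in X.B. Secondary outcomes 3 and 4 compare titration rates within a score or a measure, so they do not supply one. If one composite reaches significance and the other does not, readers will take that as different habituation, although the true effects may be equal.

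**Content changes with week.** The objective score needs tests that are not scheduled in four of the six on-treatment weeks. The analyst must either average whatever is available, which confounds test content with time, or keep only weeks 3 and 6, which loses the six-week course. The combined composite for study question 1 contains the same score. A change of content could be read as habituation or could hide it.

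**Working it through.** **The plan's own figures.** The enrollment arithmetic reproduces: 19 × 4 = 76 and 76 + 15 + 12 = 103. The 18 per group for 80% power cannot be reproduced, because X.A gives no SD, correlation, alpha or named test. This point does not depend on it.

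**Can imputation fill the gap?** X.B's imputation sentence covers dropout after week 1, not tests that were never scheduled. X.D excludes imputation for any parameter. Neither defines the objective score at weeks 1, 2, 4 and 5.

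**Effect on the curve.** Let c be the drug effect on the computerized half and n the effect on the non-computerized half, both as size of impairment against placebo. Averaging the available parts gives c at weeks 1, 2, 4 and 5, and (c + n)/2 at weeks 3 and 6. Take c = 0.24 (X.A's maximum difference), either constant or falling linearly from week 1 to zero at week 6, that is 0.24 × (6 − week)/5. The linear form is an assumption.

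| Assumed truth | Wk 1 | Wk 2 | Wk 3 | Wk 4 | Wk 5 | Wk 6 |
|---|---|---|---|---|---|---|
| Constant, n = 0 | 0.24 | 0.24 | 0.12 | 0.24 | 0.24 | 0.12 |
| Constant, n = c/2 | 0.24 | 0.24 | 0.18 | 0.24 | 0.24 | 0.18 |
| Constant, n = 2c | 0.24 | 0.24 | 0.36 | 0.24 | 0.24 | 0.36 |
| Decay, n = c (no distortion) | 0.24 | 0.192 | 0.144 | 0.096 | 0.048 | 0 |
| Decay, n = 0 | 0.24 | 0.192 | 0.072 | 0.096 | 0.048 | 0 |
| Decay, n = 2c | 0.24 | 0.192 | 0.216 | 0.096 | 0.048 | 0 |

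For the combined composite, assume equal halves and a constant subjective effect of 0.24. With constant effects the week 6 values are (0.12 + 0.24)/2 = 0.18, (0.18 + 0.24)/2 = 0.21 and (0.36 + 0.24)/2 = 0.30, against 0.24 at week 5.

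The variance changes as well. If the two halves have equal SDs and correlation r, the SD at weeks 3 and 6 is √((1 + r)/2) of that in other weeks: 0.81, 0.87 and 0.92 for r = 0.3, 0.5 and 0.7. The visit 2 covariate contains the non-computerized tests, while four of the six outcomes do not.

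**Effect on the titration-by-week test.** Simulation with 4 × 19 subjects, compound symmetry, within-subject correlation 0.4–0.8, correlation among scores 0.3–0.7, alpha 0.05 and a Greenhouse–Geisser correction (all assumed); 8,000 trials per setting. True effects are constant over weeks, scaled to 80% power for titration on the computerized score. Every rejection is therefore false.

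| Score | n = 0 or 2c | n = 0.5c or 1.5c |
|---|---|---|
| Objective, changing content | 10–14% | 6–7% |
| Combined, changing content | 6–8% | 5–6% |
| Objective minus subjective, changing content | 9–21% | 5–8% |

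Computerized-only content gives 5–6% for both the objective score and the domain difference. With n = c the changing-content objective score also shows no inflation (4–5%). Repeat simulations of the n = 0 or 2c column gave 9–16%, 6–9% and 9–25%, with the upper ends at within-subject correlation 0.8.

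**Separate tests against a direct test.** Same design, equal true effects in both domains, X.A's shape with the peak at week 1, 2 or 3 and linear decay to zero at week 6, scaled to 80% power per domain; 10,000 trials per setting. If the domains are independent, disagreement is 2 × 0.8 × 0.2 = 0.32. Simulated at within-subject correlation 0.6:

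| Objective–subjective correlation | 0 | 0.3 | 0.5 | 0.7 | 0.9 |
|---|---|---|---|---|---|
| Separate tests disagree | 0.326 | 0.281 | 0.241 | 0.201 | 0.112 |
| Direct test false positive | 0.052 | 0.050 | 0.050 | 0.052 | 0.052 |
| Direct test power, one domain affected | 0.43 | 0.61 | 0.80 | 0.97 | 1.00 |

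Within-subject correlations of 0.4 and 0.8 agree within 2 percentage points.

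**The case against.** Question 2 can be read as descriptive: it asks for a time course, the stated objective is about titration rates, and two curves may be all that was meant. Section VII.B 2h concerns only the QOLIE items, whereas the subjective composite also holds POMS and AEP. The 11–32% is an error rate only if someone infers a difference from discordant p-values, and X.B sets no such rule. All of this is fair. It makes the first gap less serious but does not supply the comparison that the question's wording invites.

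On the second gap, X.A assumes the groups are equal at week 6. The week 5 to week 6 drop is therefore a no-habituation case that departs from X.A. Under X.A's shape the week 6 distortion is zero and the distortion sits at week 3, as the decay rows show. That stands, but it moves the problem without removing it. Week 3 is the slow-titration group's assumed peak, while the 4 mg group's peak at week 1 would be read from computerized tests alone. A trial of habituation also cannot take full habituation as given.

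Within any one week all arms have the same content, so that week's between-arm comparisons are valid. This stands and limits the harm to the time course, the titration-by-week term, comparison of peaks across weeks, and objective against subjective. Secondary outcome 4 looks at individual measures over time and could expose an artefact, but it does not define the primary score.

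**Conclusion.** The concern holds, and X.B should be changed. The conflict between score definition and schedule follows from the text alone and needs no assumption: half of the objective score is scheduled in 2 of the 6 analyzed weeks, and no rule covers the other four. The absence of any objective-versus-subjective test is equally plain.

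The main harm is bias in the curve. It equals (n − c)/2 at weeks 3 and 6, which is up to 0.12 for c = 0.24 and n between zero and twice c, and it vanishes only if n = c. The rise in false titration-by-week findings is smaller: 10–14% at those extremes and 6–7% for milder imbalance in the objective score, and 5–8% overall in the combined score. The percentages rest on assumed correlations, compound symmetry and alpha 0.05, none of which the documents give.

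**What to change.** 1. For every six-week analysis, including the combined composite, build the objective score only from the computerized tests given each week, and build the visit 2 covariate from the same tests. Analyze the full-battery scores, objective and combined, at weeks 3 and 6 alongside secondary outcome 1.
2. Add one prespecified objective-minus-subjective analysis using that fixed-content score: the domain × titration × week interaction, with the difference and its confidence interval reported by week. First align all components so that higher means better, since POMS total and AEP run the other way. State one scale for both composites, for example each divided by its visit 2 SD. Keep the separate curves.
3. State which model effect answers each study question, and the status of the question 2 composites and of the added test.

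All of this uses data already collected: SAP wording, one added model and a recomputed weekly score. It does redefine the weekly primary score, so it should be settled before unblinding. MCG, SDMT and Stroop would inform only weeks 3 and 6. The weekly objective score would then cover executive function and processing speed without MCG recall, its only explicit memory test, and an effect confined to the departing tests would not be seen weekly.

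The added interaction has (2 − 1)(4 − 1)(6 − 1) = 15 degrees of freedom and no planned power: about 43% to 97% at objective–subjective correlation 0 to 0.7 if one domain alone is affected. It has only its 5% error rate against a gap that is constant over weeks, so such a gap shows only in the weekly estimates.
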